12.11 Definition of a Data Breach
A data breach is defined in the HITECH Act (43 USC 17932) as an unauthorized acquisition,
access, or use of protected health information (PHI) that compromises the security or privacy of
such information.

MiniNET_25-Oct-2024 Page 49 of 60

1091 Chapter 13: Miscellaneous Considerations

- 1092 13.1 Prohibited Medications, Treatments, and Procedures
- Participants using glulisine at the time of enrollment will be asked to contact their personal
- physician to change their prescribed personal insulin to lispro or aspart for the duration of the trial.
- The study devices (study insulin pump, study CGM) must be removed before Magnetic Resonance
- 1096 Imaging (MRI), Computed Tomography (CT) or diathermy treatment. Participants may continue
- in the trial after temporarily discontinuing use if requiring one of the treatments above.
- 1098 **13.2 Participant Withdrawal**
- Participation in the study is voluntary. Participant may withdraw at any time. For participants who
- do withdraw from the study, the study team will determine if their data will be used in analysis.
- 1101 **13.3 Confidentiality**
- For security and confidentiality purposes, subjects will be assigned an identifier that will be used
- instead of their name. Protected health information gathered for this study may be shared with the
- third-party collaborators. De-identified subject information may also be provided to collaborators
- involved in the study after the appropriate research agreement has been executed.
- 1106 **13.4 Lost to Follow Up**
- 1107 If a participant is lost to follow up and participant outcome cannot be determined, outcome
- classification will be the last known outcome/contact with the participant. A participant will be
- 1109 considered lost to follow-up after three attempted contacts that do not result in any communication
- from the participant. A certified letter may be sent as the fourth and final attempt to communicate
- 1111 with the participant.

MiniNET 25-Oct-2024 Page 50 of 60

1144

1145

1112 Chapter 14: Statistical Consideration

1113 14.1 Design and Randomization 1114 The proposed work is a safety and feasibility study of the FCL system and is not intended to be powered to fully demonstrate efficacy of the system. The sample size of up to 6 participants per 1115 session at each site was selected based on previous experience of the feasible number of individuals 1116 1117 to supervise at one time under similar study conditions. 1118 14.1.1 Planned Analysis 1119 The primary outcome of interest will be the change in the mean CGM between the week of the Usual Care observational period and the week of AIDANET at-home. This study represents a 1120 small pilot study to assess the safety and efficacy of the small-version AIDANET system and is 1121 not formally powered. Nevertheless, the randomized crossover design will allow for analysis of 1122 period effects between Group A and Group B. Comparison between these groups will be made to 1123 1124 determine if a period effect can explain part of the benefit of the FCL system during the at-home 1125 period. a. Null Hypothesis: There is no difference in the mean CGM between the week of 1126 Usual Care observational period and the at-home FCL period. 1127 1128 b. Alternative Hypothesis: There is a difference in the mean CGM between the week of Usual Care observational period and the at-home FCL period. 1129 1130 Analysis will involve use of repeated measure ANOVA models to predict CGM average and TIR 1131 with the FCL status a fixed effect and baseline HbA1c and gender as covariates. 1132 Secondary outcomes: 1133 All secondary outcomes will be similarly analyzed. If an outcomes distribution is not suited for mixed model analysis (e.g., profound skewness, or large atom at boundary) we will perform paired 1134 Wilcoxon signed rank test (and loose the capacity to use covariate) to test difference in the median 1135 instead of the mean; this is expected for time below 70mg/dL, number of hypoglycemia, and 1136 1137 possibly time above 250mg/dL. 1138 We do not plan to correct for multiple comparisons. 1139 We do not expect substantial missing values in this supervised study, but if more than 3 participants 1140 have one or more missing admissions, we will consider switching from RANOVA to mixed model repeated measures. 1141 1142 14.2 Sample Size 1143 As an early exploratory study, the goal will be to complete 6 participants to provide data from a

MiniNET 25-Oct-2024 Page 51 of 60

variety of individuals. This number was chosen out of feasibility and not from a formal power

calculation. The total sample size of 6 participants was selected based on previous experience of

- the number of participants necessary to satisfy FDA requirements for a safety and feasibility study and move onto a larger out-patient efficacy study. While this sample size is thus a convenience
- sample, we may still determine the power to analyze each of the study hypotheses based on pilot
- 1149 trial data.

1150

1151

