2.4.2 Exercise Testing

During the supervised hotel period, participants will engage in mild activity (a walk of approximately 30 minutes) on Day 2. Study staff will set a Temporary Control Rate (TCR) of approximately 50-100% starting up to approximately one hour prior to exercise for approximately 2 hours, actual TCR settings will be tailored to an individual person. Study staff will record the duration, approximate intensity (low, moderate, or high intensity), the TBR <70 mg/dL, TBR <54 mg/dL, and any episodes of Severe Hypoglycemia (SH) during the walk and in the 2 hours after the exercise challenges. Participants will be provided with an exercise monitor (e.g., Fitbit) for use during the control and FCL periods. Participants will be allowed to practice their usual exercise routine during the control and remote-monitored at-home FCL periods with use of the TCR as needed. They will not be required to record exercise events during these periods.

MiniNET 25-Oct-2024 Page 17 of 60

2.5 Study Devices Download Data from the study devices will be captured in real-time by the remote monitoring server for the

- 212 DiAs system. In addition, study devices will be downloaded at the end of the Remote-Monitored
- 213 At-Home FCL period.
- 214 **2.6 Study System Issues**
- 215 If the CGM signal becomes unavailable for more than 20 minutes consecutively, closed loop will
- 216 not operate to automatically adjust insulin delivery. If the CGM is not connected, the system will
- revert to the usual open loop function of the pump and deliver insulin with the pre-programmed
- dosing parameters. Resumption of closed-loop control will occur automatically once the CGM
- signal is again available.
- 220 If the DiAs system is unable to maintain connectivity with the Tandem t:AP pump, the pump will
- automatically revert to the pre-programmed dosing parameters after 30 minutes without any need
- for interaction from the user.

MiniNET 25-Oct-2024 Page 18 of 60

223 Chapter 3: Study Screening

- 224 **VISIT 1**
- 225 3.1 Clinical Site
- The study will be performed at the University of Virginia. Screening procedures will be performed
- either virtually or on site, at a clinical research unit, or at the hotel.
- 228 **3.2** Participant Recruitment and Enrollment
- We will enroll up to 12 participants who have been diagnosed with type 1 diabetes for at least one
- 230 year. This enrollment number accounts for dropouts or screen failures that may occur. The goal is

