- During Usual Care phase, participants will have the option of using their personal smartphone or
- receive a study smartphone to use in order to collect the data from the devices. They may also use
- their own Dexcom G6 or G7 CGM. If the participant elects to use a personal device, the Dexcom
- app will be downloaded to their phone in order to monitor the participant's CGM values and alerts
- in real-time may be used prior to initiating DiAs.

MiniNET 25-Oct-2024 Page 25 of 60

446	4.3 Blood Glucose Meter and Strips
447	4.3.1 Equipment Description
448 449	A study glucometer will be provided to all participants to wear during the entire study to record any blood glucose levels measured during the study.
450	4.3.2 Equipment Training
451 452 453	Participants will be advised to use the study glucometer when experiencing a low or high glucose values as defined in the Glycemic Treatment Guidelines. The Dexcom CGM will be calibrated, it needed, using the study glucometer and test strips in accordance with the manufacturer's labeling
454 455 456 457	If the study glucometer provides an app, the study team will request that the app be downloaded to the participant's personal phone. The app will permit continued visibility of blood glucose values to the participant and permit the study team to download the data without returning the glucometer at the end of the study.
458	4.4 Ketone Meter and Strips
459 460 461 462	Blood ketone levels will be measured during the hotel and at-home portions of the study with either the Abbott Precision Xtra Meter or the Ketomojo Meters and ketone test strips in accordance with the manufacturer's labeling. Urine ketone strips may be provided to the participant for the athemed data collection period. The glucometer component of either ketone meters will not be used
463	4.5 Study Devices Accountability Procedures
464	Device serial numbers will be recorded, and use of equipment will be tracked.
465	

MiniNET_25-Oct-2024 Page 26 of 60

Chapter 5: Randomization

467 **VISIT 2**

466

- Once eligibility is met and screening procedures are completed, the participant will proceed to
- Randomization. Participants will be randomized 1:1 to assess a 1-week usual care period before use of
- 470 the AIDANET system (Group A) or after use of the AIDANET system (Group B).
- 471 Participants who screen-fail or dropout will be replaced if it occurs prior to the Hotel Admission.
- 472 Randomization will occur via REDCap module.

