7.3 Hotel Session Check-In

- Participants will arrive at the hotel on the first day of the hotel session. The study team will perform
- 529 vital signs and inquire about any changes to the participant's medical history. Any changes to
- medical history will be communicated to the medical physician to ensure continued eligibility and
- 531 participation.
- The participant 's CGM reading, and ketone concentration will be recorded. In the event that the
- participant's CGM reading is not between 80-250 mg/dL or ketone concentration is ≥0.6 mmol/L
- prior to initiation of the FCL system, the study physician may recommend additional insulin dosing
- according to the participants' usual doses. Study physician may elect to cancel participant's
- participation in the hotel admission if concerned about their medical safety. This participant will
- 537 not be replaced.
- The participant's home insulin pump will be discontinued, and the study insulin pump will be
- initiated. The study team will ensure the proper function of the CGM and insulin pump. The CGM
- used in the study is FDA-approved for the non-adjunctive measurement of blood glucose (i.e., the

MiniNET 25-Oct-2024 Page 29 of 60

- 541 CGM reading can be used for insulin dosing decisions). The CGM readings will be the primary
- source of blood glucose values. There is no required protocol fingerstick blood glucose
- measurements other than at times of CGM calibration (if necessary) and if directed by the study
- 544 team. Fingerstick blood glucose measurements may be taken whenever participants experience
- symptoms, if the CGM glucose is suspected to be erroneous, or any time the participant would like
- to be reassured. Glycemic Treatment Guidelines to be used during the hotel admission are defined
- 547 in section 7.6.

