8.1 At Home Participant Plan

- Upon discharge on day 3 of the hotel period, participants will begin a 7 day/6-night Remote
- Monitored At-Home stage of the study. Participants will continue to wear the FCL research system
- as initiated during the hotel period. Participants will be instructed to eat approximately 3 freely
- chosen meals per day without announcing them to the system. The exception is that on 2 separate
- days participants will 1) announce all food intake (triggering an immediate BPS dose) and 2) use
- 633 their usual insulin-to-carbohydrate ratio for all food ingestion. Participants will be instructed to
- participate in their usual level of physical activity. Participants will complete the study after lunch
- on overall study day 9 (Day 7 of the home portion), at which point they will return to use of their
- usual diabetes care.
- Participants in Group A will complete the study after this 1-week FCL data collection period.
- Participants in Group B will then begin the Usual Care control period for data comparison (see
- 639 section 6.1).

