14.3 Outcome Measures

14.3.1 Primary Efficacy Endpoint

- The primary metric for analysis will be change in mean CGM between the second last 7 days week
- of the control Usual-Care period and the one-week Remote Monitored At-Home FCL period.

1154 **14.3.2 Secondary Outcomes**

- Glycemic Metrics will be obtained directly from CGM data and will include the standard metrics
- recommended by the international consensus on CGM including mean CGM, GMI derived from
- mean CGM, time in range 70-180 mg/dL, CGM standard deviation (StDev), CGM coefficient of
- variation (CV), CGM %<54 mg/dL, CGM %<70 mg/dL, CGM %>180 mg/dL, and CGM %>250
- 1159 mg/dL. For the Usual Care period, CGM data will be obtained from either the participant's
- personal CGM or a study provided CGM. Data for the control Usual-Care period will be analyzed
- by last available 7-day period. During the FCL period, CGM data will be obtained directly from
- the study device. As GMI is a linear transformation of mean CGM, this metric will have the same
- effect and will be presented as a primary outcome as well. All other glycemic metrics will be
- 1164 considered secondary outcome measures.
- Device-Use Metrics will include time in automation, total daily insulin dose, and number of
- boluses per day. During the Usual Care period, participants using an insulin pump will have their
- pump uploaded at the end of the period to capture their insulin delivery and bolus data. The FCL
- period, insulin use, and bolus data (if any) will be captured from the experimental device.
- Exercise Challenge Metrics will include the duration of exercise, approximate intensity of exercise
- (low, moderate, or high intensity), the % CGM<70 mg/dL, % CGM<54 mg/dL, and any episodes
- of SH (CGM<70mg/dL for more than 15 minutes with interruption, CGM≥70, of less than 15
- minutes or CHO treatment) during and 2 hours after the exercise challenges.
- 1173 Unannounced Meal Metrics during the supervised house/hotel FLC stage participants will be
- instructed to eat at least 3 meals per day. The time of completion for these meals will be recorded
- by study staff. The % CGM>250 mg/dL for the 4 hours after each meal will be recorded and
- specifically analyzed. Participants will be instructed to freely eat meals during the supervised at-
- home FCL stage but will not be required to record the timing of the meals for unannounced meals.

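### The primary crossover model has no period term, although the plan asks whether period explains the FCL benefit; the separate Group A versus Group B comparison is not said to adjust the FCL estimate

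*Combined protocol and SAP*

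**What the plan says.** Section 14.1.1 makes the change in mean CGM between the usual-care week and the at-home AIDANET week the primary outcome. It says Groups A and B will be compared to "determine if a period effect can explain part of the benefit of the FCL system during the at-home" period. No statistic is named for that comparison, and nothing says what its result does to the FCL estimate.

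The only model given is a repeated-measures ANOVA for mean CGM and TIR "with the FCL status a fixed effect and baseline HbA1c and gender as covariates". Secondary outcomes follow the same model or a paired signed-rank test. If more than three participants "have one or more missing admissions, we will consider switching from RANOVA to mixed model repeated measures"; the terms of that fallback model are not listed. No other section adds a period or sequence term.

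On balance between sequences:
- Chapter 5 states 1:1 allocation through REDCap, without a block size, and "Participants who screen-fail or dropout will be replaced if it occurs prior to the Hotel Admission".
- Section 7.3 says a participant whose admission is cancelled at check-in is not replaced.
- Section 3.2 allows up to 12 to be enrolled to complete about 6: "This enrollment number accounts for dropouts or screen failures that may occur".
- Section 14.3.4 computes an outcome only when at least 80% of the window's CGM readings are available. Section 14.3.2 softens this for usual care, which is analysed "by last available 7-day period".

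**The concern.** The plan raises a rival explanation for its main result and then specifies a model that cannot separate the two. The study is a pilot that is not formally powered, so the false-positive rate is not the main issue. What matters is whether the reported FCL estimate and interval can be read free of period.

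If completers are equally split, a period shift cancels from the point estimate but goes into the residual and widens the interval. If they are unequal, part of the shift is also reported as FCL effect. A non-significant Group A versus Group B comparison would reassure nobody, because at this size it misses most shifts up to 1 SD.

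**Working it through.** **Inputs.** From the plan: two sequences, 1:1, six completers, model terms as above. Assumed, because the documents give no values: period shift π (second week minus first) of 0.33, 0.5, 0.67 or 1.0, in SDs of the paired difference; two-sided 5%; no carry-over. The plan states no power or precision figure to reproduce.

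**Estimators.** Let d = FCL minus usual care and τ the FCL effect. Group A has FCL second, so E(d) = τ + π. Group B has FCL first, so E(d) = τ − π.
- Without period: the mean of d has expectation τ + π(nA − nB)/n, on n − 1 df.
- With period: (mean d in A + mean d in B)/2 has expectation τ. Its SE is s·√(1/nA + 1/nB)/2, with s pooled within sequence, on n − 2 df.

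**Covariates.** HbA1c (taken at screening) and gender add the same amount to both of a participant's weeks and drop out of d. In a simulated 4:2 data set with complete pairs, the FCL coefficient was −14.11 with or without them; adding period changed it to −18.16.

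**Group A versus Group B power.** Noncentral t on n − 2 df, noncentrality 2π/√(1/nA + 1/nB). At 3:3 and π = 0.5 this is 1/√(2/3) = 1.22 on 4 df, giving 16%.

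**Half-width at 3:3 with no period effect.** The mean of s is √(2/ν)·Γ((ν+1)/2)/Γ(ν/2) true SDs: 0.952 at ν = 5 and 0.940 at ν = 4.
- Without period: 2.571 × 0.952/√6 = 1.00 SD.
- With period: 2.776 × 0.940 × √(2/3)/2 = 1.07 SD.

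With π nonzero, the unadjusted residual sum of squares is noncentral chi-square with noncentrality 4π²·nA·nB/n, which is 6π² at 3:3. Mean half-widths come from numerical integration. FCL power (true effect 1.5 SD) comes from 400,000 simulated trials per setting.

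| π (SD) | A-v-B power 3:3 | A-v-B power 3:2 | Half-width at 3:3, without / with period | FCL power at 3:3, without / with |
|---|---|---|---|---|
| 0 | 5% | 5% | 1.00 / 1.07 | 83% / 78% |
| 0.33 | 10% | 8% | 1.06 / 1.07 | 80% / 78% |
| 0.5 | 16% | 12% | 1.14 / 1.07 | 75% / 78% |
| 0.67 | 24% | 18% | 1.24 / 1.07 | 68% / 78% |
| 1.0 | 46% | 33% | 1.50 / 1.07 | 50% / 78% |

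**Unequal and smaller splits.** The RMSE break-even solves 1/n + π²((nA − nB)/n)² = (1/nA + 1/nB)/4.

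| A:B | Bias without period | Half-width at π = 0, without → with | Adjusted interval narrower above π of | Adjusted RMSE lower above π of |
|---|---|---|---|---|
| 3:3 | 0 | 1.00 → 1.07 | 0.34 | same estimate |
| 3:2 | π/5 | 1.17 → 1.34 | 0.51 | 0.46 |
| 4:2 | π/3 | 1.00 → 1.13 | 0.51 | 0.43 |
| 2:2 | 0 | 1.47 → 1.91 | 0.70 | same estimate |
| 3:1 | π/2 | 1.47 → 2.20 | 1.08 | 0.58 |
| 5:1 | 2π/3 | 1.00 → 1.43 | 1.23 | 0.55 |

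At π = 0.5 the bias is 0.5/5 = 0.10 SD at 3:2 and 0.5/3 = 0.17 SD at 4:2. RMSE without and with period is then 0.458 and 0.456 at 3:2, and about 0.44 and 0.43 at 4:2. At π = 1.0 it is 0.49 and 0.46, and 0.53 and 0.43.

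Unadjusted coverage stays at or above 95% at 3:2 (95.7–98.7%), 4:2 (95.3–97.5%) and 3:1 (95.0–96.3%). At 5:1 it falls to 90% at π = 0.67 and 87% at π = 1.0. Adjusted coverage was 94.9–95.1% throughout.

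**How likely is imbalance?** The documents do not settle this. If allocation were simple, six participants would split exactly 3:3 with probability 20/64 = 31%, 4:2 either way 47%, 5:1 either way 19% and 6:0 3%. Blocking would improve on this, but later losses could still unbalance completers.

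**The case against.** The plan does not ignore period. Comparing within-person differences between sequences is the standard test of period in this design, and the wording of Section 14.1.1 need not be an exhaustive list of model terms. On that reading, only a sentence linking the comparison to the FCL estimate is missing.

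The harm is also small in the likeliest cases. At 3:3 there is no bias and the unadjusted interval is conservative; at π = 0.33 the half-widths are practically equal, and at π = 0.5 the RMSEs at 3:2 and 4:2 barely differ. After losses the adjusted interval is often the wider one. The bias is conditional on the realised split: under 1:1 allocation with losses unrelated to sequence, it averages to zero. This is a six-person feasibility study, and a period term does not remove carry-over.

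All of this stands as a limit on importance. It does not supply the missing link. A weak test that leaves the estimate untouched does not show how much of the FCL benefit is period, and a bias that averages out over hypothetical allocations is still present in the one that occurs. Keeping the unadjusted estimate as a sensitivity analysis deals with the precision argument.

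**Conclusion.** The point holds. The stated model omits the factor that the plan itself offers as a rival explanation, and the planned comparison neither adjusts the estimate nor has the power to dismiss period. At 3:3 the consequence is lost precision once the shift exceeds about 0.34 SD. At unequal splits the estimate is biased by π(nA − nB)/n; the gain in RMSE from adjusting is negligible near 0.5 SD and clear near 1 SD at 3:2 and 4:2.

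The missing term and the bias formula do not depend on assumed values; every size in SD units does. The change is worth making, but its absence does not invalidate the study.

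**What to change.** - In Section 14.1.1, add period (first or second) as a fixed effect beside FCL status, with participant as the repeated or random factor. HbA1c and gender may stay.
- Report the period-adjusted FCL estimate and the period estimate, each with its 95% interval, instead of relying on the Group A versus Group B test. With complete pairs these are (mean d in A + mean d in B)/2 and (mean d in A − mean d in B)/2.
- Report the unadjusted paired estimate with its interval as a sensitivity analysis.
- List the same terms for the mixed-model fallback and name a small-sample df method such as Kenward-Roger.
- If all completers share one sequence, period cannot be estimated: report the unadjusted estimate and say so.
- State carry-over as a limitation. Section 8.1 says "Participants in Group B will then begin the Usual Care control period for data comparison" directly after AIDANET use, and a period term does not address that.

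The cost is SAP wording and one error df; order is already recorded. With no true period effect the mean half-width rises from 1.00 to 1.07 SD at 3:3, and by more after losses, as tabulated. FCL power at 3:3 for a 1.5 SD effect falls from 83% to 78% with no period effect, but then stays at 78% whatever the shift.
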